12.4 Analysis for Long-term Effects

Analysis for long-term effects will be descriptive in nature. As the selection bias resulting from confounding by indication for this study could be very large, and as some impacts are not measurable, comparative analyses will be inherently challenging to interpret. For these reasons any comparative analyses must be considered as exploratory for signal detection and for the purpose of hypothesis generation. The incidence rates of clinically significant bleeding (inpatient and outpatient) and/or rescue medication use will be described for the Exposed Cohort and Unexposed Cohort:

- Kaplan-Meier survival curves will be constructed for patients with bleeding events for the Exposed Cohort and Unexposed Cohort.
- As needed, a Cox model with romiplostim exposure as a time-varying covariate will be used to compare the total event-free survival rates among exposed ITP patients and the unexposed cohort, with an estimation of the relative risk and associated 95% confidence interval. This analysis will adjust for potential confounders and propensity scores. Stratification by propensity score, significant year spans, and country may be considered for this analysis, although such an analysis will only be for exploratory and hypothesis generating purposes. Other treatment exposures,

health status, and disease conditions may also be considered for inclusion in the model as time-varying covariates.

Comparison of platelet counts in predefined time periods (prior to, during, immediately after treatment cessation, and post treatment) between the Exposed Cohort and Unexposed Cohort:

- Mean and SD
- As needed, a multiple regression will be used to test the difference between the Exposed Cohort and Unexposed Cohort. However, such an analysis will only be for exploratory and hypothesis-generating purposes.

Comparison of long-term safety (eg, thromboembolic risk, thrombocytosis, hematological malignancies, focused upon AML, and MDS), including:

- Description of rare and long latency events: Some events (eg, AML and MDS) are too few to conduct any meaningful statistical analysis or comparison. The study will provide detailed case descriptions for each case observed.
- Incidence rate of these events will be calculated.

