Patient records will provide person-years of data for each study cohort (Exposed and Unexposed). The incidence rates will be assessed for both the exposure and non-exposure cohorts. The incidence rates will also be assessed for both the follow-up time periods prior to and after the initial date of receiving romiplostim in the Exposed Cohort.

When sample size permits, Kaplan-Meier survival curves will be constructed for patients with events of interest for the Exposed Cohort and Unexposed Cohort.

Due to the intrinsic limitations of this type of observational study, the effects of confounding by indication may bias the results when the incidence rates of study outcomes are compared between the Exposed Cohort and Unexposed Cohort. The effects associated with confounding by indication will be considered in all analyses in order to reduce the possible impact of these effects in the comparison.

In order to reduce the effects of confounding by indication, a propensity score will be developed for each adult chronic ITP patient. A stratified analysis (by propensity score strata, disease severity, and platelet count) and multiple regression analyses will be carried out. As needed, the age-, sex-, and propensity score-matched approach may be also applied to the adult chronic ITP study population. (Inherent limitations related to propensity score are addressed in [Section 8](#)).

Cox regression models using romiplostim exposure as a time-varying covariate may be used to compare the event rates among ITP patients and the reference cohort, with an estimation of the hazard ratio and associated 2-sided 95% confidence interval. Other treatment exposures, health status, and disease condition may also be considered for inclusion in the model as time-varying covariates. The analysis will adjust for potential confounders and propensity score. Multiple event models such as Andersen-Gill models may be used to evaluate recurrent events if applicable. However, this analysis is only intended to serve exploratory and hypothesis generation purposes.

Means and 95% confidence intervals of laboratory numerical outcomes (eg, platelet counts) will be obtained and compared between the associated cohorts, and among different predefined time periods related to romiplostim treatment ([Section 7.1](#)).

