- A hypothetical concern regarding hematopoietic growth factors is that they may enhance the growth of existing malignancies or promote the growth of new malignancies that are influenced by the receptor-ligand axis. The TPO receptor is predominantly expressed on cells of the myeloid lineage, and there is no confirmed expression on solid tumors ([Graf et al, 1996](#); [Columbyova et al 1995](#)); therefore, it is not expected that romiplostim will promote the growth of solid tumors. In the ITP clinical program, there is no evidence of increased neoplasia, including hematopoietic malignancies; there is, however, a potential risk that TPO receptor agonists may stimulate the progression of existing hematopoietic malignancies or MDS among patients with thrombocytopenia caused by conditions other than ITP. Ongoing clinical studies in other patient populations, including MDS, will help to assess this potential risk.

Other potential risks include:

- Thrombotic/thromboembolic complications
- Progression of increased reticulin to an irreversible BM fibrotic state

In Europe, the product label includes further dose adjustment rules that have been specified by the European regulator as a risk minimization measure of thromboembolic risk and have not been tested in clinical trials.

Dose adjustment rules as specified in the European label

Platelet count (x 10 ⁹ /L)	Action
<50	Increase once weekly dose by 1 mcg/kg
>150 for 2 consecutive weeks ^a	Decrease once weekly dose by 1 mcg/kg
>250 ^a	Do not administer, continue to assess platelet count weekly After the platelet count has fallen to < 150 x 10 ⁹ /L, resume dosing with once weekly dose reduced by 1 µg/kg

^a Due to the inter-individual variable platelet response, in some patients platelet count may abruptly fall below 50 x 10⁹/L after dose reduction or treatment discontinuation. In these cases, if clinically appropriate, higher cut-off levels of platelet count for dose reduction (200 x 10⁹/L) and treatment interruption (400 x 10⁹/L) may be considered according to medical judgment

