5. DATA COLLECTION PROCEDURES

5.1 Primary Data Collection

The primary data collection for the NCPRR is dependent upon the NHRS. All citizens in Denmark, Sweden, and Norway are included in the systems, and all health care information for each citizen will be included in the system databases. For this reason the NCPRR will not need to actively collect data directly from patients.

Patients with a NHRS diagnosis of ITP of 6 months duration or more are selected for abstraction of medical records and collection of details of the medical history including romiplostim exposure. If a patient was not seen in hospital (in-patient or out-patient

contact, including hematology clinic visits) at least once during the reporting period, the charts for that patients for that reporting period will not be reviewed. When the patient re-appears in the hospital database in following reporting periods, the chart abstraction will resume for that patient.

Because ITP is a diagnosis of exclusion and secondary causes of thrombocytopenia may be difficult to diagnose, some patients will require review of medical records and laboratory data including bone marrow exams, if any, prior to their first diagnosis of ITP (ICD-10: D69.3-D69.4). These will include the relevant time periods prior to their first diagnosis of ITP for all patients who have a history of any condition from [Appendix 2](#) prior to the first diagnosis of ITP.

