5.4 Ascertainment for Laboratory Data Outcomes

The effect of romiplostim on thrombocytosis and worsened thrombocytopenia after cessation of romiplostim therapy will be assessed based upon laboratory data. The NHRS contains all laboratory testing results. The study will review all electronic laboratory results through 4 predefined romiplostim study time periods. Two types of data will be obtained: 1) average level of platelet counts for each predefined time period; and 2) frequency of platelet counts above or below the normal range for each predefined time period. Thrombocytosis will also be confirmed by electronic medical chart review, and will be assessed whether it occurs with an adverse experience or not. In addition, rescue medication data for thrombocytopenia will also be obtained, and will be used to adjust for treatment effects in different study periods.

5.5 Standard Review of BM Biopsies and Related Study Plan for Patients with BM Biopsy

BM biopsy-related secondary endpoints of the NCPRR will be based upon all ITP patients who have at least 1 BM biopsy stained for reticulin and collagen registered in the National Pathology Registry (SNOMED: T06000, T06001, T06002 and/or S45410). For the purpose of NCPRR BM study requirements, all BM specimens for adult chronic ITP patients will be requested to be stained for reticulin and collagen.

To ensure these standards, 2 pathologists will independently re-review all BM biopsy specimens. If diagnostic conclusions for a BM biopsy from both pathologists are inconsistent, a third pathologist will re-review the specimen to achieve a final diagnosis. All reviews will be blinded to romiplostim treatment status.

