7.3 Time at Risk

Time at risk for the NCPRR is defined as from time after initial romiplostim exposure to occurrence of outcomes listed in [Section 6.2](#). For patients without these study outcomes, the time at risk will be from the index date to death, loss to follow-up, or the end of study, whichever comes first.

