Case ascertainment and confirmation: Diagnosis based on ICD-10 codes may not be able to correctly determine outcomes. The sensitivity and specificity of diagnosis based on ICD-10 codes for different diseases and conditions and for different cohorts may vary, and may induce a bias. To address this issue, the study will review electronic medical charts to confirm a diagnosis beyond ICD-10, as well as laboratory data and BM biopsy as needed.

Selection bias due to missing values: The study is based on the NHRS databases. Information for some key covariates (eg, laboratory data) may be missing for some patients. It is possible to introduce a selection bias if patients with missing values are excluded from a particular analysis. The missing value issue may also occur in development of propensity score. Patients with missing values will be excluded from the propensity development model. To address this issue, statistical methods will be employed: 1) to evaluate the mechanism of the “missingness” and 2) to impute values for missing variables based on patterns of “missingness”, if necessary.

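### Thrombocytosis is compared between cohorts as a rate per calendar person-time with no allowance for how often platelets are counted, so the comparison can be biased upward for romiplostim

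*Protocol*

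**What the plan says.** Section 12.4 has an item headed "Comparison of long-term safety (eg, thromboembolic risk, thrombocytosis, hematological malignancies", and under it "Incidence rate of these events will be calculated". The Statistical Considerations in the synopsis give the denominator: "Patient records will provide person-years of data for each study cohort (Exposed and Unexposed". They add that rates are assessed in both cohorts and, within the Exposed Cohort, before and after the first dose. Section 7.3 makes this calendar time. For patients without the outcome, "the time at risk will be from the index date to death, loss to follow-up, or the end of study".

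Section 6.2 defines thrombocytosis as a laboratory count above 450 x 10⁹/L among adult chronic ITP patients. The objective in Section 1.2 is narrower and names romiplostim-treated patients only. Section 5.4 takes the counts from routine results ("The NHRS contains all laboratory testing results") and adds confirmation of thrombocytosis by chart review.

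On count frequency, the protocol offers only the European dose-adjustment table in Section 2.3. One row acts on counts in two consecutive weeks. The row for counts above 250 reads "Do not administer, continue to assess platelet count weekly". No frequency is stated for unexposed or pre-romiplostim time. Section 8 names four key bias sources; testing frequency is not among them.

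**The concern.** A transient rise above 450 is recorded only if a sample falls inside it. Where counts are dense most episodes are seen, and where they are sparse many are missed. The missed episodes leave the numerator, but the untested time stays in the denominator. If count frequency follows treatment, a rate ratio mixes the drug's effect with the intensity of looking.

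The comparison is labelled exploratory, but its stated purpose is signal detection, and Section 3.1 provides for an urgent ad hoc report if a significant risk is observed. The caution in Section 12.4 concerns confounding by indication, which is a different problem.

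The protocol already accepts the principle for bone marrow. Section 5.3 declines to estimate the incidence of fiber content because biopsies are not routine, and Section 12.6 uses only the first result because of bias from repeated testing. Platelet counts get no comparable protection.

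**Working it through.** **The study's denominator.** Section 11 and Appendix 1 give 89% power at 0.5% background incidence and relative risk 2.
- Exact conditional test of two Poisson rates, 0.025 per tail (assumed; no alpha is given with the table), 12,700 and 4,234 person-years: 89.6%. This method matches 29 of the 30 cells of Appendix 1 within 2 points. The exception (2.0%, relative risk 1.50: 99 stated, 94.2 computed) does not bear on this point.
- Normal-approximation two-proportion test on the same person-years: 91.4%. On patients (1,860 and 623): 30.9%.

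So the study is sized on person-time, for relative risks of 2 to 4.

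**Detection model.** Inputs:
- Exposed interval: 7 days, inferred from the table in Section 2.3.
- Unexposed interval I: not stated; assumed 14, 28 or 91 days.
- Episode duration D: not stated; assumed 14 days, with 7 and 28 as a range.
- Timing of counts independent of the platelet level.

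P(found) = min(1, D/I)

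Apparent ratio = true ratio x P(found, exposed) / P(found, unexposed)

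With a true ratio of 1 and D = 14, exposed detection is min(1, 14/7) = 1. Then:
- I = 14: 14/14 = 1, ratio 1.0
- I = 28: 14/28 = 0.50, ratio 2.0
- I = 91: 14/91 = 0.154, ratio 6.5

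At 28 and 91 days the ratio is 4.0 and 13.0 for D = 7, and 1.0 and 3.25 for D = 28.

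**Dilution.** Time at risk continues after treatment stops. If half of exposed time is counted weekly and half at the unexposed interval, the ratio at I = 28 is (0.5 x 1 + 0.5 x 0.5)/0.5 = 1.5. At I = 91 it is (0.5 + 0.5 x 0.154)/0.154 = 3.75.

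**In events.** Assume a true rate of 2 per 100 person-years in both cohorts, D = 14 and I = 28.
- Exposed: 4,234 x 0.02 = 84.7 found
- Unexposed: 12,700 x 0.02 x 0.5 = 127 found
- Ratio 2.0; 95% CI 2.0 x exp(±1.96 x √(1/84.7 + 1/127)) = 1.52 to 2.63

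That interval excludes 1 although there is no true difference.

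**Two candidate remedies, at I = 91.**
- *Count only quarters with at least one test.* Every 91-day quarter in both cohorts contains a count, so no time is removed and the ratio stays 6.5.
- *Use one random count per patient-quarter.* The chance that it exceeds 450 is 0.02 x 14/364 = 0.00077 in both cohorts. Expected positives are 4,234 x 4 x 0.00077 = 13.0 and 12,700 x 4 x 0.00077 = 39.1, a ratio of 1.0 with 95% CI exp(±1.96 x √(1/13.0 + 1/39.1)) = 0.53 to 1.87. The frequency-driven bias is gone, at the price of fewer events.

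**The case against.** The strongest reply is that the documents fix neither the size nor the presence of an inflation. That stands. No unexposed count frequency is given, and eligible patients are on continuing ITP treatment or have had a splenectomy, so sparse testing cannot be presumed. The explicit weekly instruction covers only the period when dosing is withheld; weekly counting on drug more generally is inferred from the rule on consecutive weeks. If episodes outlast the unexposed interval the factor is 1.0.

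A reader might also infer more than the text supports:
- *That a year without hospital contact yields no laboratory data.* Section 5.1 says only that "the charts for that patients for that reporting period will not be reviewed". Section 5.4 separately reviews all electronic laboratory results, so what lapses is chart confirmation.
- *That Sections 5.4 and 8 contradict each other.* Section 8 says "Information for some key covariates (eg, laboratory data) may be missing for some patients". That concerns covariates, so the conflict is weak.
- *That all blood-count endpoints share the defect.* Mean platelet counts are not person-time rates. Leukocytosis with anemia is reached only by the synopsis's general sentence on rates in both cohorts.

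Two further replies carry less weight. The drug is meant to raise platelets, so equal true rates are unlikely; but the detection factor multiplies whatever the true ratio is. Section 12.9 promises to separate missing values from tests not done; but it does not take untested time out of the denominator, and chart review cannot recover a count never drawn. Nor can a propensity score built on the 6 months before the Index Date balance monitoring that follows from treatment.

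Sampling windows could be left to a SAP. The comparison, its calendar denominator and the list of biases are in the protocol.

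**Conclusion.** The concern holds in conditional form. The protocol sets up a thrombocytosis comparison per calendar person-time, between cohorts and before versus after first dose, with no allowance for unequal testing. The result can be biased upward for romiplostim. With equal true rates, 14-day episodes and weekly exposed counts the apparent ratio runs from 1.0 to 6.5 over unexposed intervals of 14 to 91 days, and off-drug time reduces it. Several of these values lie in the range of 2 to 4 that the study is sized to detect. Episode duration and unexposed interval are assumptions, so the text does not support saying that the ratio is inflated, only that it may be and that the plan could not tell. The rate within treated patients, taken as description, is not in dispute.

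**What to change.** 1. Beside every thrombocytosis rate, report platelet tests per patient-year by cohort and by Section 7.1 period.
2. In Section 12.4, make any between-cohort or before/after comparison at a common sampling frequency. One way is one randomly chosen count per patient-quarter, reported as the proportion of sampled quarters above 450 and not as incidence. Alternatively, restrict thrombocytosis to description in romiplostim-treated patients, as the objective in Section 1.2 words it.
3. Keep the all-counts incidence rate as the descriptive figure for treated patients.
4. Add testing frequency to the bias sources in Section 8.

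Restricting person-time to quarters with at least one count is not a substitute. Apply the same approach to leukocytosis with anemia only if it is compared between cohorts.

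The cost is wording and programming on data already held, and wider intervals in the thinned comparison. Bias from symptom-triggered testing remains and should be stated as a limitation.

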12.5 Description of Transient Worsened Thrombocytopenia After Romiplostim Treatment Cessation

The analysis will be conducted for the Exposed Cohort in chronic ITP patients.

The comparison will be based upon platelet counts among four predefined study time periods ([Section 7.1](#)).

- Comparison of mean (SD) platelet counts in four study time periods between study cohorts.
- Multiple regression to determine if the phenomenon of transient worsened thrombocytopenia exists after adjusting for other potential confounders and propensity scores. The propensity score-stratified analysis will also be used.

12.6 Comparisons of Outcomes that are Dependent on BM Data

1) Frequency and incidence of increased BM reticulin and/or BM fibrosis with associated clinical signs⁵, confirmed by findings in a BM biopsy and 2) frequency and incidence of collagen fibrosis with associated clinical signs confirmed by findings in BM biopsies will be analyzed between the Exposed Cohort and Unexposed Cohort in all adults with chronic ITP:

⁵ Clinical signs: any of the following: splenomegaly, hepatomegaly, leukocytosis, and cytopenia.

- Since the sample size could be very small, the detailed description of each identified case will be listed in the report.
- If there is a sufficient sample size, a formal statistical analytic comparison, as described in [Section 12.4](#), will be conducted.

Description of prevalence rate of reticulin and collagen formation among chronic ITP patients:

- This analysis will be conducted based upon all eligible adult chronic ITP patients in the period prior to romiplostim treatment by splenectomy status. Only initial BM results will be used in the analysis to reduce potential selection bias caused by repeated testing for BM with abnormal findings.
- Prevalence of patients with reticulin and collagen formation in BM will be assessed. No comparison will be conducted; however, the descriptive analysis will be used to describe demographic characteristics, clinical features, and laboratory findings.

1) Frequency and incidence of chronic idiopathic myelofibrosis (primary myelofibrosis) according to the WHO diagnostic criteria, and 2) overall and specific incidence rates of BM fibrosis findings, including reticulin and collagen fiber content formation, and chronic idiopathic myelofibrosis in the Exposed Cohort and Unexposed Cohort in adult chronic ITP patients who have BM data prior to and post romiplostim therapy:

- Since the sample size could be very small for these outcomes, the detailed description of each identified case will be listed in the report.
- If there is a sufficient sample size (e.g., approximately 10 per treatment group for each covariate considered), a formal statistical analytic comparison, as described in [Section 12.4](#), will be conducted.

2) Association of splenomegaly and/or hepatomegaly with BM fibrosis and 2) association of changes in peripheral blood prior to and following the finding of reticulin and collagen fiber content or formation (reticulin grading 1 to 3):

- The association tests will be based on data 3 to 6 months prior to, 0 to 3 months prior to, 0 to 3 months post, and 3 to 6 months post-positive findings in BM biopsies.
- 2XN tabulation will be created and chi-square tests for categorical variables will be used to test the association.
- Multiple regression and logistic analysis will be used to investigate romiplostim's effect after adjusting for other confounders, if feasible.

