1.2 Secondary Objectives

Potential clinical risks:

- To describe the phenomenon of worsened thrombocytopenia (platelet count significantly reduced to, or below, baseline platelet count levels) after romiplostim cessation among adult chronic ITP patients
- To study the incidence rate of thrombocytosis (platelet count $> 450 \times 10^9/L$) among romiplostim-treated adult chronic ITP patients with/without adverse events
- To describe the incidence rate of thrombotic/thromboembolic events and the distribution of specific diagnoses of these thrombotic/thromboembolic events for a romiplostim-exposed cohort and an unexposed cohort
- To assess the incidence rate of hematological malignancies and pre-malignant states (focused on acute myelogenous leukemia [AML] and myelodysplastic syndromes [MDS]) for a romiplostim-exposed cohort and an unexposed cohort
- To describe clinically significant bleeding and/or receipt of rescue medication (any new ITP medication prescribed to a chronic ITP patient during romiplostim therapy) in predefined romiplostim therapy periods ([Section 7.1](#))
- To describe the incidence rate of concurrent leukocytosis and anemia (measured by laboratory test results taken within 4 weeks of each other)

³ Clinical signs: any of the following: splenomegaly, hepatomegaly, leukocytosis, and cytopenia

- To describe patient safety profiles, including the incidence rate of renal failure among adult chronic ITP patients with renal impairment medical condition when romiplostim therapy is initiated
- To measure the impact of the EU dosing rule in the cohort of romiplostim exposed patients

Potential BM abnormal findings:

- To describe the prevalence of reticulin and collagen fiber content in the first BM biopsy of adult chronic ITP patients prior to romiplostim exposure, by splenectomy status
- To assess the incidence of collagen fibrosis with associated clinical signs confirmed by findings in BM biopsies of adults with chronic ITP either receiving or not receiving romiplostim
- To study the incidence of chronic idiopathic myelofibrosis (CIMF, primary myelofibrosis) according to the WHO diagnostic criteria in adults with chronic ITP either receiving or not receiving romiplostim

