5.3 Case Ascertainment for BM Abnormality

Cases of BM fibrosis with associated clinical signs will be ascertained using electronic medical record review that will be blinded to romiplostim exposure status. Confirmation of the diagnosis of BM fibrosis will be verified by an evaluation of the results of BM biopsies and clinical presentation.

Reticulin and collagen fiber content information will be gathered from BM biopsies. Since BM biopsies are not routinely obtained when treating ITP patients, an estimate of the incidence rate of reticulin and collagen fiber content from this study would likely be inaccurate. For this reason the prevalence rate of reticulin and collagen fiber content and related grading among patients with BM biopsies stained for reticulin and collagen formation will be calculated. Only data from the first BM biopsy prior to romiplostim therapy will be included in the analysis to reduce bias. This analysis will be conducted by splenectomy status.

Adult chronic ITP patients in both the Exposed Cohort and Unexposed Cohort with both positive findings of reticulin and collagen fiber content and repeated BM biopsies will be

assessed to describe disease progression related to changes in reticulin and collagen fiber content in subsequent BM biopsies.

Incidence of BM abnormal findings (eg, PMF, reticulin, and collagen fiber content formation) will be assessed based upon only patients with BM data prior to and post romiplostim therapy.

The relationship between BM findings of reticulin and collagen fiber content and clinical/laboratory findings will be established using data 6 to 3 months prior to, 3 to 0 months prior to, 0 to 3 months post, and 3 to 6 months post-abnormal BM findings (please see [Section 12.9](#) regarding issues related to missing data).

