6.2 Outcomes

There are many outcomes in the NCPRR. They are:

Primary Outcome Endpoints:

- Incidence of increased BM reticulin and/or BM fibrosis with associated clinical signs⁴, confirmed by findings in BM biopsies among adult chronic ITP patients
- Incidence of reticulin and collagen BM fibrosis (reticulin fibrosis and collagen fibrosis: SNOMED codes: M49000, M49001, M49020, M99611) with associated clinical signs, confirmed by findings in a BM biopsy among adults chronic ITP patients

Secondary Endpoints:

Clinical Endpoints:

- Average platelet counts prior to, during, immediately after treatment cessation, and following romiplostim therapy (study periods are defined in [Section 7.1](#))
- Incidence of thrombocytosis (laboratory confirmation of a platelet count $> 450 \times 10^9/L$) with/without adverse events among adult chronic ITP patients
- Incidence of thrombotic/thromboembolic events (ICD-10: 180, 126)
- Incidence of hematological malignancies (focused on AML and MDS)
- Incidence of clinically significant bleeding and/or receipt of rescue ITP medications for each predefined romiplostim treatment period ([Section 7.1](#))
- Incidence of concurrent leukocytosis and anemia (measured by laboratory test results taken within 4 weeks of each other)
- Description of platelet counts and dose adjustment in mcg/kg of romiplostim in patients with cITP according to dose adjustment rules specified in the European SPC

⁴ Clinical signs: any of the following: splenomegaly, hepatomegaly, leukocytosis, and cytopenia.

BM Endpoints:

- Prevalence of reticulin and collagen fiber content in the first BM biopsies of adult chronic ITP patients prior to romiplostim therapy by splenectomy status
- Incidence of collagen fibrosis with associated clinical signs confirmed by findings in BM biopsies among adult chronic ITP patients
- Incidence of PMF (primary myelofibrosis) (ICD-10: c94.5) according to the WHO diagnostic criteria in adult chronic ITP patients who have BM data prior to and/or post romiplostim therapy
- Overall and specific incidence of BM fibrosis, including reticulin and collagen fiber content formation, and PMF among adult chronic ITP patients with BM data prior to and/or post romiplostim therapy
- Association between the aforementioned primary and secondary clinical outcomes and BM abnormal findings

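### The protocol does not settle who is at risk for incident marrow findings, and the primary outcome has no baseline, so fibre present before romiplostim can be counted as a new event

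*Protocol*

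**What the plan says.** The primary objective (Protocol 1.1) is an incidence rate of increased reticulin and/or marrow fibrosis, with a clinical sign and biopsy confirmation, in romiplostim-treated adults with chronic ITP. Four sections bear on who can contribute such an event.

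- **12.6, primary outcome and collagen fibrosis with signs:** these "will be analyzed between the Exposed Cohort and Unexposed Cohort in all adults with chronic ITP". No marrow data before treatment are required.
- **12.6, primary myelofibrosis and overall or specific fibrosis:** here the set is restricted to both cohorts "in adult chronic ITP patients who have BM data prior to and post romiplostim therapy".
- **5.3:** the incidence of marrow abnormalities, with reticulin among the examples, "will be assessed based upon only patients with BM data prior to and post romiplostim therapy". The same section says biopsies are not routine in ITP and that "an estimate of the incidence rate of reticulin and collagen fiber content from this study would likely be inaccurate".
- **6.2, primary myelofibrosis and overall or specific fibrosis:** "adult chronic ITP patients who have BM data prior to and/or post romiplostim therapy".
- **7.3:** "Time at risk for the NCPRR is defined as from time after initial romiplostim exposure to occurrence of outcomes". No condition of being outcome-free at the start is attached.

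The protocol treats pre-treatment fibre as worth measuring. One secondary objective (1.2) is "To describe the prevalence of reticulin and collagen fiber content in the first BM biopsy of adult chronic ITP patients prior to romiplostim exposure".

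**The concern.** An incidence rate needs a population that could still acquire the finding and a rule for recognising that it is new. For the primary outcome the protocol gives neither. A patient whose marrow is first examined after starting romiplostim, and who already had increased reticulin, meets the definition if any clinical sign is present. So does a patient whose earlier biopsy showed the same grade, because confirmation under 5.3 rests on biopsy results and clinical presentation without reference to an earlier slide.

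This rate is the main deliverable of the registry, and 12.6 expects very few cases. A handful of pre-existing findings could make up much of the numerator. If treated patients are biopsied more often than untreated ones, the excess would look like a drug effect.

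**Working it through.** **1. The protocol's own denominator.** From 3.5:

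- Prevalent cases: 570 × 13 = 7,410; × 0.20 = 1,482; × 0.95 = 1,408; × 0.25 = 352.
- Incident cases: 5,700 × 0.20 = 1,140; × 0.95 = 1,083; × 0.25 = 271.
- Exposed: 352 + 271 = 623, as stated. The stated 4,234 patient-years imply 4,234 / 623 = 6.8 years each.
- Unexposed: 1,408 + 1,083 − 623 = 1,868, against 1,860 stated.

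The denominators are not in dispute. The question is what enters the numerator.

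**2. The at-risk set, section by section.**

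| Outcome | 5.3 | 6.2 | 12.6 |
|---|---|---|---|
| Primary (increased reticulin/fibrosis with signs) | before and after, if read literally | no biopsy-timing condition | all adults |
| Primary myelofibrosis; overall/specific fibrosis | before and after | before and/or after | before and after |

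The sections disagree in both rows. A condition tied to romiplostim dates also has no meaning for patients who never receive it, although 12.6 applies it to both cohorts.

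**3. Do other provisions remove pre-existing fibre?**

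- *Appendix 2 through 3.4.2.* It lists myelofibrosis (C94.5), myeloproliferative disorder (D47.1), MDS (D46) and haematological malignancies (C81-C96). It works on ICD-10 diagnoses, does not list reticulin or collagen findings or the SNOMED codes of 6.2, and its window closes 6 months after the qualifying ITP diagnosis. The Index Date may be years later.
- *Clinical signs.* Any one of four suffices. Cytopenia is one of them and is not limited to new onset or to cell lines other than platelets, in patients selected for a low platelet count.
- *Blinded re-reading (5.5).* This standardises each slide but does not compare a later slide with an earlier one.
- *Case narratives (12.2, 12.6).* These may reveal an old finding, but no rule takes it out of the rate.

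**4. Index Date in unexposed patients (4.1).** For those diagnosed on or after 01 April 2009 it is the diagnosis date. A work-up biopsy at or soon after diagnosis can then fall in time at risk. For an exposed patient, the same biopsy would ordinarily precede the first dose.

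**5. Possible size.** The protocol gives no biopsy rate or prevalence, so both inputs are assumptions. Let *b* be the share of the 623 exposed patients biopsied after index and *p* the share of those with pre-existing fibre, with every such patient having a qualifying sign. Misclassified events = 623 × *b* × *p*; the added rate divides by 4,234.

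| *b* | *p* | Events | Per 1,000 patient-years |
|---|---|---|---|
| 5% | 5% | 1.6 | 0.37 |
| 10% | 10% | 6.2 | 1.47 |
| 20% | 20% | 24.9 | 5.89 |
| 20% | 30% | 37.4 | 8.83 |

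**6. Unequal biopsy frequency.** Assume a true rate of 1 per 1,000 patient-years in both cohorts, *p* = 10%, and 10% of the unexposed biopsied. The unexposed rate becomes 1 + 1,000 × (1,860 × 0.10 × 0.10) / 12,700 = 2.46.

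- Exposed biopsied 10%: 1 + 1.47 = 2.47; ratio 1.0.
- Exposed biopsied 20%: 1 + 2.94 = 3.94; ratio 1.6.
- Exposed biopsied 30%: 1 + 4.41 = 5.41; ratio 2.2.

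**The case against.** The best reply is that 5.3 already supplies the missing step, since it confines marrow incidence to patients with data before and after treatment. In context that sentence fits the secondary endpoints, and 12.6 sets the primary outcome in all adults. If it is meant to cover the primary outcome, the two sections contradict each other. Either way the text needs correcting.

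Several stronger readings are tempting but not supported:

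- *That the plan removes nobody with earlier disease.* Appendix 2 does remove diagnosed myelofibrosis and related disorders. The gap is narrower: biopsy findings without such a diagnosis, and anything arising after its window closes.
- *That the first pre-treatment biopsy is the baseline for the primary outcome.* The sentence "Only data from the first BM biopsy prior to romiplostim therapy will be included in the analysis to reduce bias" governs the prevalence analysis only.
- *That the protocol concedes its primary rate is inaccurate.* The caution in 5.3 concerns fibre content on biopsy and is answered there by estimating prevalence. The primary outcome also needs a clinical sign.
- *That time in patients never biopsied does not belong in the denominator.* Such a patient can develop signs, be biopsied and become a case. All-patient time is a legitimate denominator for a clinically detected event.

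It also stands that the study is descriptive, comparisons are exploratory, and each case is described. That limits the damage to inference but does not correct the reported rate. The illustration applies no reduction for the clinical sign, so within each pair of assumptions it is an upper figure.

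**Conclusion.** The point holds in this form: three sections disagree on who is at risk for incident marrow findings, and the primary outcome has neither a stated reference for *increased* nor an outcome-free condition at index. Pre-existing fibre can be counted as incident; the documents do not show that it will be, or how often. Under the assumed 5%/5% to 20%/30% range, with a qualifying sign in all, the effect is about 2 to 37 events in 4,234 patient-years. The apparent rate ratio stays near 1 if biopsy frequency is equal between cohorts and moves away from it if not. This goes beyond missing detail, because the rate concerned is the sole primary objective and the protocol already plans to collect and re-read the slides needed to separate new from old findings.

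**What to change.** 1. Reconcile 5.3, 6.2, 7.3 and 12.6 so that each marrow outcome has one stated at-risk set, expressed relative to the Index Date so that it applies to both cohorts.
2. For the primary outcome, keep the clinical-sign requirement and define *increased* against the most recent available pre-index biopsy, as re-read under 5.5.
3. Do not count as incident a finding already present at equal or higher grade before index.
4. Report the primary rate in all patients, split into confirmed-new or progressed cases and cases with unknown baseline, with and without the latter.
5. Beside each rate, print the number of patients biopsied and biopsies per 100 patient-years, by cohort.
6. For unexposed patients whose Index Date is the diagnosis date, treat the diagnostic work-up biopsy as the baseline and not as an incident finding.

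The cost is protocol wording and a few table columns. No new biopsies are needed, and the re-reading is already planned. The price is fewer confirmed incident cases and a wider interval, with some cases left in the unknown-baseline line because biopsies are not routine.
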